## Subject recruitment plan

Under Substudy 1, we plan to recruit 22 subjects (11 subjects per site at Emory and the University of Alabama at Birmingham) with cystic fibrosis carrying a partial function mutation genotype not covered or expected to be covered by an FDA approved treatment with a CFTR modulator. Under Substudy 2, we plan to recruit 20 subjects encoding N1303K CFTR to Emory and UAB (10 subjects per site). In both substudies we intend to include ~50% female and ~50% male subjects age  $\geq 12$ . Subjects will first be recruited from the cities participating in the trial (Atlanta and Birmingham), and CF physicians have previously expressed interest in discussing the proposed clinical trial with eligible individuals. Study investigators also have immediate access to a robust national patient registry through the Cystic Fibrosis Foundation therapeutic development network, and (following IRB approval) will contact cystic fibrosis physicians caring for individuals with the appropriate genotypes to ask whether these patients might be interested and/or willing to discuss possible study participation (including consent) with one of the lead investigators on the proposed trial ([name], [name], [name], [name]).

All individuals who consent to participation will be evaluated at one of two clinical CF care centers (Emory, University of Alabama in Birmingham). Travel, meals, accommodations, etc. for study visits will be covered by funds available through the project, and an incentive payment of \$150 per visit will be provided as a gift card or check. For minors who participate in the study, travel expenses, etc. will also be provided for one parent and the gift card or check for each visit provided to that parent (i.e., not the minor). For adult subjects accompanied by a caregiver, travel expenses, etc. will also be provided for the caregiver.

### 7. Informed Consent Process:

Informed consent will be obtained by well-trained study coordinators or investigators using an Institutional Review Board approved document. Parents/guardians/participants will be asked to sign the informed consent documents only after the study has been fully described to the subject and all questions have been answered. Participants will be offered at least 24 hours to review the consent/assent before the research is to begin, although consent may be obtained on the day of screening if preferred by study subjects (eg those traveling from significant distance).

Assent for minors will be obtained by experienced study personnel with many years expertise in this area. Minors will be informed about the study using age appropriate, and easily understood language. Care will be taken to assure minors: 1) Are very comfortable with the study, 2) Are under no pressure to enroll or participate, and 3) Understand they can withdraw at any time without penalty or change in their medical care. The investigator obtaining consent/assent will provide a written summary of the interaction for inclusion with the patient's research file.

The participant's parent/guardian will be asked to read and review the document. The investigator will explain the research study to the participant and parent/guardian and answer any questions that may arise. A verbal explanation will be provided in terms suited to the parent/guardian and participant's comprehension of the purposes, procedures, and potential risks of the study and of a subject's rights as a participant. Participants and parent/guardian will have the opportunity to carefully review the written consent form and ask questions prior to signing. The participants and parent/guardian will have the opportunity to discuss the study with their family and/or think about the consent document prior to agreeing to participate. Participants and parent/guardian will be informed that participation is voluntary

and that they may withdraw from the study at any time, without prejudice. A copy of the informed consent/assent document will be given to the parent/guardian/participants for their records. The informed consent process will be conducted and documented in the source document (including the date), and the form signed, before the participant undergoes any study-specific procedures. The rights and welfare of the participants will be protected by emphasizing to them that the quality of their medical care will not be adversely affected if they decline to participate in this study. Parents of subjects under the age 18 will sign the consent form with separate assent signed by children participating in the study, as applicable.

CF is a life long illness, and patients/families are typically very sophisticated regarding the nature of CF care -- including clinical trial participation. The disease is not associated with cognitive or other intellectual limitations. No vulnerable adult subjects are intended for enrolment in the trial. If, in the opinion of the study investigator, a prospective participant lacks sufficient understanding and is therefore not able to provide informed consent, that subject will not be enrolled. The ability to obtain consent represents criteria for inclusion in the trial.

#### 8. Compensation for time and effort:

Travel, meals, accommodations, etc. for study visits will be covered by institutional or other funds and an incentive payment of \$150 per in-person visit and \$30 at the Day 7 telephone call will be provided as a gift card or check. All payments will be pro-rated. For minors who participate in the study, travel expenses, etc. will also be provided for one parent and the gift card or check for each visit provided to that parent (i.e., not the minor). For adult subjects accompanied by a caregiver, travel expenses, etc. will also be provided for the caregiver. An incentive payment of \$150 will also be provided if an unscheduled visit is needed (for multiple repeat assessments or cutaneous punch biopsy occurring on another day). If the unscheduled visit is needed just for a repeat laboratory sample collection, an incentive payment of \$30 will be provided.

#### 9. Study Discontinuation

Criteria for discontinuing the study intervention (e.g., halting rules), may include any monitoring test(s) and associated clinical decision point(s) which in the opinion of the clinical investigator, qualified designee, or Data Safety Monitoring Board are viewed as placing the patient at significant risk if Trikafta™ administration is to continue. This could include, for example (but is not limited to) worsening liver function or abnormalities associated with Trikafta™ administration. Discontinuation from Trikafta™ does not mean discontinuation from the study, and remaining study procedures should be completed as indicated by the study protocol. If a clinically significant finding is identified (including, but not limited to changes from baseline) after enrollment, the investigator or qualified designee, and/or Data Monitoring Committee (DMC) (also referred to as Data Safety Monitoring Board, DSMB) will determine if any change in participant management is needed. Any new clinically relevant finding will be reported as an adverse event (AE).

The data to be collected at the time of study intervention discontinuation will include:

- All measurements described for the day 56 follow-up/washout visit

Participants are free to withdraw from participation in the study at any time upon request.

An investigator may discontinue or withdraw a participant from the study for the following reasons:

- If any clinical adverse event, laboratory abnormality, or other medical condition or situation occurs such that continued participation in the study would not be in the best interest of the participant
- Disease progression which requires discontinuation of the study intervention
- If the participant meets an exclusion criterion (either newly developed or not previously recognized) that precludes further study participation
- Participant is unable to receive Trikafta™ for 3 days.
- Pregnancy
- Significant study intervention non-compliance

The reason for participant discontinuation or withdrawal from the study will be recorded. An attempt will be made to replace subjects who sign the informed consent form and receive Trikafta™, and subsequently withdraw, or are withdrawn or discontinued from the study.

A participant will be considered lost to follow-up if he or she fails to return for any scheduled visit and is unable to be contacted by the study site staff.

The following actions will be taken if a participant fails to return to the clinic for a required study visit:

- The site will attempt to contact the participant and reschedule the missed visit within 2-5 days, and counsel the participant on the importance of maintaining the assigned visit schedule and ascertain if the participant wishes to and/or should continue in the study.
- Before a participant is deemed lost to follow-up, the investigator or designee will make every effort to regain contact with the participant (where possible, 3 telephone calls and, if necessary, a certified letter to the participant's last known mailing address or local equivalent methods). These contact attempts should be documented in the participant's medical record or study file.
- Should the participant continue to be unreachable, he or she will be considered to have withdrawn from the study with a primary reason of lost to follow-up.

## 10. Data Safety Monitoring Plan

Oversight for this trial will be performed by a DSM Chair. A Data Safety Monitoring Board (DSMB) will be selected in consultation with the Chair to specifically oversee the clinical study. The DSMB will consist of at least two physicians experienced in treating patients with cystic fibrosis, a DSMB coordinator and a biostatistician. The DSMB Chair will convene a protocol conference call with committee members so that the DSMB can approve the monitoring plan and review any concerns regarding the current protocol prior to initiation of study enrollment.

The DSMB is primarily responsible for reviewing safety data which will be provided on a continual basis throughout the performance of the study as well as reviewing interim analyses report after four patients have completed the 28-day study drug administration, and again following 50% enrollment (completion of 11 subjects in Substudy 1 and 10 subjects in Substudy 2). The DSMB may recommend early termination or modification of either trial substudy for reasons of study subject safety. Subjects will be monitored for adverse events (AEs) and serious adverse experiences (SAEs) by the Investigators, the study sites' Institutional Review Boards, and the DSMB. The DSMB will also provide recommendations needed to assist the investigative team.

One goal of the present study is to provide clinical data that will support a correlation between IPS CFTR activity and clinical benefit of a CFTR modulator. In the present study, the highest level of stringency will be applied. This will include: 1) DSMB, as described above, 2) detailed interim evaluations, 3) generation of case report forms for all study subjects, 4) detailed statistical analysis, tabular summaries, and leading edge evaluation to test clinical benefit, 5) compiling data in SAS or other well-accepted formatting, 6) discussions with interested parties (e.g. Vertex and CF Foundation) to provide updates regarding clinical trial progress, and 7) timely publication of data, etc. Logistical support and resources of the type intended here are provided by the Institution and the Department of Pediatrics for physician-sponsored clinical trials at Emory. Our intent will be to furnish a clinical profile that provides high stringency and rigor. We recognize that for the present clinical trial data will not be used for submission to FDA or towards label expansion of Trikafta™. However, by providing a compelling data set and offering this information early and openly to Vertex, interested third-party insurers, CFF, as well as CF patients and their families, we will furnish information that will help guide more extensive studies of IPS cell analysis among patients with rare forms of the disease.

**Study Monitoring:** The Emory University self-monitoring tool will be customized to fit the needs of the current study. This tool will be utilized by the study team for monitoring the progress of the trial, and assuring data accuracy and protocol compliance. Study monitoring will take place at least once a year.

Clinical site monitoring is conducted to ensure that the rights and well-being of trial participants are protected, that the reported trial data are accurate, complete, and verifiable, and that the conduct of the trial is in compliance with the currently approved protocol/amendment(s), with International Conference on Harmonisation Good Clinical Practice (ICH GCP), and with applicable regulatory requirement(s). The self-monitoring process and study team will visually inspect study records collected since each previous monitoring visit. The scope of the monitoring shall include the informed consent process, eligibility, CRFs, biological specimen tracking and AE reporting.

Quality control (QC) procedures will be implemented beginning with the data entry system. Data QC checks that will be run on the database will be generated. Any missing data or data anomalies will be communicated to the site(s) for clarification/resolution.

A designated member of the study team will provide the completed self-monitoring tool to the study PI and team within 7 days of the monitoring visit. The study PI will document receipt and review of the monitoring report, resolutions and/or corrective actions to findings on the Site Monitoring Log. The monitoring reports will be shared between sites, with the Emory Clinical Trials Audit and Compliance (CTAC) office, and with the DSMB. Protocol deviations/violations will be reported to the Emory IRB per reporting guidelines and will be reviewed by the DSMB in a timely fashion or during regular meetings, as needed.

This study may be temporarily suspended or prematurely terminated if there is sufficient reasonable cause. Written notification, documenting the reason for study suspension or termination, will be provided by the suspending or terminating party to study participants, investigators, NIH, and any other regulatory authorities. If the study is prematurely terminated or suspended, the Principal Investigator (PI) will promptly inform study participants, the Institutional Review Board (IRB), and will provide the reason(s) for the termination or suspension. Study participants will be contacted, as applicable, and be informed of changes to study visit schedule.

Circumstances that may warrant termination or suspension include, but are not limited to:

- Determination of unexpected, significant, or unacceptable risk to participants
- Insufficient compliance to protocol requirements
- Data that are not sufficiently complete and/or evaluable
- Determination that the primary endpoint has been met
- Determination of futility

#### 11. Statistical Methods For a proposed open-label prospective 4-week trial of Trikafta™.

**Substudy 1:** Patients with CF or CFTR-dependent illness who do not have access to modulator therapy but exhibit a clinical phenotype suggestive of partial/residual CFTR activity.

We will serially evaluate clinical outcomes of interest prior to and after the start of therapy. Change in clinical measurements (spirometry, weight/BMI, quality of life, sweat chloride) will be monitored. Our main goals are to determine the clinical response to Trikafta™ and to determine if *in vitro* responsiveness of iPS cells predicts clinical response. The primary outcome is response to Trikafta™ after 4 weeks of treatment. In this study a clinical response to Trikafta™ at week 4 of treatment will be defined as an improvement, from baseline, in  $FEV_1 > 5\%$  predicted and each subject will be classified a responder or non-responder. In this study, if at least 40% of subjects meet the definition of responder, the drug will be considered efficacious (i.e., comparable to the benefit which led to Orkambi™ approval by FDA following trials in F508del homozygotes). Overall response rate will be accompanied by an approximate binomial 95% confidence interval. To determine the role of iPS *in-vitro* response to Trikafta™, we will compare the  $\Delta Isc$  (change in  $Isc$ ) among Trikafta™ responders and Trikafta™ non-responders using a two-sample t-test or a Wilcoxon rank sum test if distributions are skewed. Additionally, we will correlate the  $\Delta Isc$  obtained from *in vitro* experiments with the change in  $FEV_1\%$  predicted (post minus pre) using Spearman's rank-order correlation with an associated 95% confidence interval. We will also test whether the iPS response reaches a CFTR functional threshold of 40% wild-type levels (a magnitude of activity in primary airway epithelial cells viewed as potentially relevant to clinical benefit). In a sensitivity analysis, we will replicate the  $FEV_1$  analysis with sweat chloride responses, and determine the *in vivo* response rate.

For other outcomes of interest including sweat chloride levels, quality of life, and weight/BMI, we will apply a mixed effect model to examine the change in these measures over the study duration. Models will include a subject-specific intercept, to account for variability among subjects prior to the start of the treatment, and a categorical variable for time (baseline, day 14, day 28, day 56). A Dunnet's post-hoc comparisons procedure will be used to determine which time points demonstrated a significant change from baseline. Using the same mixed effects models, we will include  $\Delta Isc$  as predictors of *in vivo* improvement. We will also test the interaction between time and  $\Delta Isc$  to determine when *in-vitro* response is most associated with change in clinical response. Adverse events and other safety endpoints will be tabulated and reported using counts and percentages or means and standard deviations, as appropriate.

In addition, because clinical parameters may vary among patients prior to the start of therapy, we will also approach the analysis using a modified N of 1 design configured for the purpose of comparing iPS studies in contrast to the aggregate analysis described above. Using the framework of single subject research, we will evaluate therapeutic response in individual subjects by an interrupted time series (ITS) approach. Briefly, in the absence of an independent control group, ITS analysis is a quasi-experimental design in which each subject acts as their own control and is followed serially in time prior to and after an interruption (in this case, the start of treatment). If the treatment has causal

impact, the post-intervention time series will have a different level or slope than the pre-intervention series. Time series models also have the power to test and correct for possible cyclical patterns and outliers. Using segmented regression analysis, we will conduct ITS models for each of the subjects enrolled in the trial. A significant change in slope from the pre-treatment period will indicate a significant treatment effect. ITS models will be constructed for each outcome of interest where historical and pre-treatment data are available. The change in slope will also be correlated with the *in-vitro* response using Spearman's rank-order correlation coefficient.

All analyses will be conducted using the intention to treat principal, where all subjects will be included in analysis regardless of how long they took the study medication. Statistical significance will be assessed at the 0.05 level and analyses conducted using SAS v. 9.4 (SAS Institute; Cary, NC).

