#### Sample size

The FDA has suggested that scientifically meaningful 'binning' of patients based on clinical characteristics can help guide future approval of specific patient groups for drug treatment. The present study is not intended for FDA submission or label expansion of Trikafta™, but as a means to determine whether iPS cells differentiated to respiratory phenotype can be used to predict clinical response to CFTR modulators. For the purposes of this protocol, the subjects enrolled, although potentially of different genotypes, will represent a scientifically meaningful cohort or 'bin' of individuals with partial function mutations, sweat chloride < 80 mmol/L, and/or pancreatic sufficiency. This protocol is designed to compare *in vitro* responsiveness of differentiated iPS cells to *in vivo* clinical activity of Trikafta™, and will test the null hypothesis that the true Trikafta™ response rate of CFTR individuals with partial function mutation genotypes is  $\leq 10\%$  vs. the alternative hypothesis that the true Trikafta™ response rate is  $\geq 40\%$ . We will initially enroll four subjects, and expect all of these individuals will show a clinical response (e.g.,  $> 5\%$  improvement of % predicted FEV1 from baseline). If none of the first four subjects exhibit a response, the study will be terminated. Otherwise, we intend to enroll a total sample size of 22 individuals. Subjects who do not complete the study will be replaced. In this design, if Trikafta™ is ineffective, the probability of early termination after four subjects is 66% and only a 5% chance of concluding the drug is effective (type I error). If Trikafta™ is effective, there is an 86.4% chance of reaching this conclusion. If fewer than four patients show a clinical effect, Trikafta™ will be considered ineffective. To demonstrate the ability of iPS cells to predict clinical benefit, 22 patients will provide at least 80% power to detect a significant correlation of at least  $r = 0.55$  between the changes in clinical outcomes with changes in short circuit current as measured in iPS cells. Tabular details of this analysis are provided below. Power calculations were performed using PASS v. 14 (Kaysville, UT) with a two-sided Z-test and a significance level of 0.05.

	Cumulative # of responses	Decision	95% Confidence Interval (CI)

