Stage 1: Enter 4 subjects	0	Terminate the trial because the agent is ineffective. Response rate is <math>\leq 10\%</math>	LB of 95% CI is $< 10\%$
	At least 1	Inconclusive result, continue trial (proceed to stage 2).	95% CI contains 10% and the UB is $< 40\%$

Stage 2: Enter 18 additional subjects	4 or less (stage I + stage II)	Consider that the agent is ineffective. Response rate is $\leq 10\%$	LB of 95% CI is less than 10%
	5 or more (stage I + stage II)	Drug may be effective Response rate is greater than 10% and not different from 40%	95% CI contains 40% and LB is $> 10\%$
	14 or more (stage I + stage II)	Drug is effective Response rate is at least 40%	95% CI LB $\geq 40\%$

LB = Lower Bound, UB = Upper Bound

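### The formula for the Substudy 1 response-rate interval is not named; if it is the normal approximation, it collapses to 0–0% when the trial stops at 0 of 4

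*Combined protocol and SAP*

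**What the plan says.** Section 11, Substudy 1, makes response at week 4 the primary outcome and classes each subject as a responder or non-responder. On reporting it says "Overall response rate will be accompanied by an approximate binomial 95% confidence interval". It gives no formula and does not mention the two-stage design.

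The sample-size text sets up that design. It "will test the null hypothesis that the true Trikafta™ response rate of CFTR individuals with partial function mutation genotypes is" at most 10%, against "the alternative hypothesis that the true Trikafta™ response rate is" at least 40%. On the first stage it says "If none of the first four subjects exhibit a response, the study will be terminated", and then "Otherwise, we intend to enroll a total sample size of 22 individuals".

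The decision table ties response counts to statements about a 95% interval. With 0 of 4 it gives an interval statement too, so an interval at that outcome is foreseen. In the row "5 or more (stage I + stage II") the interval is said to contain 40% and to have a lower bound above 10%. At 14 or more its lower bound is said to be at least 40%.

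**The concern.** The normal approximation is the ordinary reading of an approximate binomial interval. Its half-width is proportional to √(p̂(1 − p̂)), which is zero when no subject responds. The design makes that outcome common, because 0 of 4 is exactly what ends the trial early.

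A report of a stopped trial could then show a response rate of 0% with a 95% interval of zero width. Four subjects cannot support that: the exact interval at 0 of 4 runs from 0% to 60.2% and includes the 40% target. The protocol plans to share results with the manufacturer, insurers, the CF Foundation and families, so the precision attached to an early stop matters.

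**Working it through.** **Inputs.** From the sample-size text: first stage of 4, stop at 0 of 4, otherwise 18 more for a total of 22; null rate 10%, target rate 40%. From the decision table: success at 5 or more of 22. The interval formula is not given, so three are tried: normal approximation (Wald), Wilson score and exact (Clopper-Pearson).

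**The plan's own figures.** The text gives "the probability of early termination after four subjects is 66% and only a 5% chance of concluding the drug is effective (type I error") and "If Trikafta™ is effective, there is an 86.4% chance of reaching this conclusion".
- Early stop at 10%: 0.9⁴ = 0.656, which matches 66%.
- Type I error with 5 or more of 22: 4.4%, against 5% stated.
- Power with 5 or more of 22: 85.6%, against 86.4% stated.

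The design enumerated here is therefore the one described, within small differences. Coverage does not depend on the success cut-off.

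**Intervals at 0 of 4.**
- Normal approximation: 0 ± 1.96 × √(0 × 1 / 4) = 0% to 0%.
- Wilson: 0% to 49.0%.
- Exact: upper limit 1 − 0.025^(1/4) = 60.2%, so 0% to 60.2%.

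**Coverage over the whole design.** For true rate p,

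C(p) = (1 − p)⁴ × [p lies in the 0/4 interval] + Σ P(x; p) × [p lies in the x/22 interval], x = 1 to 22,

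where P(x; p) sums Bin(a; 4, p) × Bin(x − a; 18, p) over a = 1 to 4.

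| True rate | P(stop at 0/4) | Normal, whole design | Normal, given 22 reached | Wilson, whole design | Exact, whole design |
|---|---|---|---|---|---|
| 10% | 65.6% | 34.0% | 98.9% | 95.6% | 98.6% |
| 20% | 41.0% | 56.5% | 95.6% | 98.2% | 98.2% |
| 30% | 24.0% | 71.8% | 94.4% | 95.6% | 98.0% |
| 40% | 13.0% | 83.5% | 95.9% | 96.4% | 97.5% |
| 50% | 6.3% | 89.2% | 95.2% | 89.2% | 98.6% |

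At 10% the normal interval gains nothing from stopped trials. It gains 34.0% from continued ones, out of a possible 100 − 65.6 = 34.4%, and 34.0/34.4 is about 99%. At 40% it gains 83.5% out of a possible 100 − 13.0 = 87.0%, and 83.5/87.0 is about 96%. Nearly the whole shortfall is the 0/4 outcome.

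Wilson drops to 89.2% at 50% for a related reason: its upper limit at 0 of 4, 49.0%, falls just short of 50%.

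**Which interval does the decision table imply?** Lower bounds at 5 of 22 are 5.2% (normal), 10.1% (Wilson) and 7.8% (exact). The table requires more than 10%, and of these only Wilson meets it. At 14 of 22 the lower bounds are 43.5%, 43.0% and 40.7%, so all three meet the 40% requirement. The first-stage row for at least one responder requires an upper bound below 40%; at 1 of 4 the upper bounds are 67.4%, 69.9% and 80.6%, so none fits.

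**The case against.** The strongest reply is that the plan never commits to the normal approximation, and that its decision table counts against it. The row for 5 or more responders fits Wilson (10.1%) and not the normal approximation (5.2%). This stands. The 34.0% and 83.5% figures are conditional on a formula that the documents do not name, and they should not be read as the coverage of the interval as planned.

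A reader might also infer that coverage fails because the interval ignores the early stop. The numbers do not support that. The Wilson and exact intervals ignore the stop in the same way and still cover at least 95.6% at 10–40%.

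A third reply is that the loss falls only on trials already declared ineffective by count, and that a zero-width interval on four subjects is visibly odd. This lowers the consequence but does not make the interval valid.

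A reader might also want a bias-adjusted response rate. The crude rate averages 35.8% at a true 40%, but that comes from counting stopped trials as 0%. Given that 22 are reached, the average is 0.358/0.870 = 41.1%, a bias of +1.1 points. No correction is needed at the target rate.

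**Conclusion.** The point holds as a conditional one and is minor. The interval method is unnamed, and its ordinary reading gives 0–0% at an outcome with probability 66% at a true rate of 10% and 13% at 40%. Under that reading, coverage over the whole design is 34.0% and 83.5%. Under Wilson it is 95.6–98.2% at 10–40% but 89.2% at 50%. Only the exact interval stays above 95% at all five rates in the table.

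The result assumes independent responses with a common rate, the 4 + 18 design as written, and an interval computed on whichever sample the trial ends with. Decisions rest on response counts, so no decision changes. What is at stake is the precision reported with the primary outcome after an early stop.

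**What to change.** In Section 11, Substudy 1, replace the approximate interval with the exact (Clopper-Pearson) 95% interval, computed on the final sample of 4 or 22. At true rates of 5%, 10%, 20%, 30%, 40%, 50% and 60% it covers 97.4–98.7% over the whole design. At the least, name a score interval and rule out the normal approximation.

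Keep the response-count rule as the decision rule. Amend the confidence-interval column of the decision table to match the chosen method: the exact lower bound at 5 of 22 is 7.8%, not above 10%, and the first-stage row for at least one responder needs correcting under any of the three methods.

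The cost is one sentence, the table edits and a slightly wider interval. At 9 of 22 the exact interval is 20.7–63.6%, against 20.4–61.5% for the normal approximation.
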